Minimization. To minimize risks due to tDCS, all participants will be carefully screened prior to tDCS for contraindications to tDCS. Those with a history of mood symptoms suggesting risk for hypomania or bipolar disorder will be excluded. Use of an electrically isolated power source (i.e., battery-powered DC stimulation device) also protects against delivery of more intense currents than intended. Participants with lesions or open wounds on the scalp will be excluded. Participants will be closely observed for signs of skin burns, discomfort, or other stress. During stimulation sessions, participants will be closely monitored to ensure the electrode sponges stay moist with saline (to enhance conductivity) and in good contact with the scalp in order to help prevent burns. Participants will have the option of discontinuing the study at any time and will be explicitly instructed to inform the tDCS administrator immediately if they experience any discomfort. The tDCS administrator will inform the supervising physician about any participant who has significant discomfort or a skin lesion that emerges after tDCS delivery. A Butler Neuromodulation Research Facility covering physician is available during all procedures to evaluate any participant or research staff identifying a concern related to study procedures. If there is any doubt about the mental or physical status of an individual before or after testing, the supervising physician will evaluate the participant and make a recommendation for cancelling the research procedure and /or arranging follow-up care, as indicated. Telephone or in-person follow-up will be arranged as needed and will not be considered a protocol deviation. Any participant that has experienced adverse effects will be evaluated, treated as necessary, and withdrawn from the study if deemed necessary.

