In order to assess for and monitor presence and tolerability of adverse effects, we will use a modified version of a tDCS Side Effects Questionnaire informed by Brunoni and colleagues¹¹. This is a 10-item measure that assess such effects as headache, neck pain, scalp pain, skin redness, sleepiness, difficulty concentrating, and acute mood changes. The measure will be administered after each tDCS session. For each item, participants are asked to report how bothersome each symptom on the form has been with response options "None," "Mild," "Moderate," or "Severe." For any item rated "severe," or any item which appears to significantly increase in severity over the course of the session, the evaluator will notify the covering physician immediately and the covering physician will provide further evaluation as medically necessary. tDCS administrators are encouraged to contact the covering physician about any additional tDCS related concerns and this will not be considered a protocol deviation. Reported side-effects endorsed will be reviewed during weekly meetings of study staff. Follow-up or further evaluation will occur as necessary.

In addition, in order to monitor participant safety during the intervention period, we will also have participants complete self-report measures to assess for increased manic or hypomanic symptoms (from the Altman Self-Rating Mania Scale (ASRM)). The ASRM will be administered at baseline and prior to the first and last session of tDCS (sessions 1 and 5). Scores ≥ 6 will be considered clinically significant and will require evaluation by a study clinician. Further, we will assess significant changes in affect such as anxiety/activation/anergia/sedation from the PANAS scale at the baseline and week 2 follow-up assessment. Lastly, changes in frequency and dosage of any medication will be monitored at every participant contact time point. The study physician will monitor affective symptom changes and make determinations as to whether the participant should discontinue the intervention and receive additional mental health treatment.

Risks due to FMRI.

Risks. The primary FMRI contraindications are claustrophobia, metal implants, and pregnancy. Some individuals may experience discomfort from loud noises inside the scanner.

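### Cheap improvement: the ASRM, the only described mania screen with a cut-off, is never given after the last tDCS session; add it at the existing week 2 assessment

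*Combined protocol and SAP*

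**What the plan says.** Section 7.a (Risks due to tDCS) names hypomania induction as a risk reported when tDCS was used to treat depression. Under Minimization, the plan adopts the ASRM "in order to monitor participant safety during the intervention period". The schedule is: "The ASRM will be administered at baseline and prior to the first and last session of tDCS (sessions 1 and 5". Scores of 6 or more "will be considered clinically significant and will require evaluation by a study clinician".

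Other safeguards are described alongside it:

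- **Screening.** Section 2.c excludes bipolar disorder, and section 7.a adds: "Those with a history of mood symptoms suggesting risk for hypomania or bipolar disorder will be excluded".
- **Side-effects questionnaire.** It follows every session and includes an acute mood item. For a severe rating, or "any item which appears to significantly increase in severity over the course of the session, the evaluator will notify the covering physician immediately".
- **SAFTEE.** It is used at each session (section 6.a, 6.c).
- **PANAS.** The plan assesses "anxiety/activation/anergia/sedation from the PANAS scale at the baseline and week 2 follow-up assessment".
- **Physician judgement.** "The study physician will monitor affective symptom changes and make determinations as to whether the participant should discontinue the intervention", and whether more mental health treatment is needed. A physician also evaluates the participant if there is "any doubt about the mental or physical status of an individual before or after testing".

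A week 2 assessment is already scheduled in both UG3 and UH3 (section 6.a, 6.c).

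**The concern.** The sponsor chose a mania scale with an explicit trigger for a risk that it names, but two of the three planned readings come before any stimulation. The third comes before the last dose, and no reading follows the completed course. The schedule also fixes the last reading to session 5 by number, so a participant who stops earlier is never screened after exposure begins. The plan itself expects some missed sessions as participants move from a structured programme to the community (section 2.a, 2.b).

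What is at stake is detection of an uncommon mood event. After the last session, detection rests on general instruments and clinical judgement, without the specific trigger that the sponsor adopted.

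**Working it through.** The plan states no figure to reproduce here. The check counts readings against the session schedule.

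**Inputs.** ASRM at baseline and before sessions 1 and 5, with cut-off 6 (section 7.a). Five sessions of 20 minutes, which may spread over 10 days (section 2.a, 2.b). UH3 attrition of 20% across the sessions and the first two scans, with 100 enrolled; UG3 enrolment of 60 (section 2.d).

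**Step 1: readings after stimulation starts.** Only the reading before session 5 qualifies.

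| Last session attended | Now | With one added reading, if attended |
|---|---|---|
| 1, 2, 3 or 4 | 0 | 1 (after treatment has stopped) |
| 5 | 1 | 2 (one after the full course) |

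**Step 2: exposure at the one qualifying reading.** 4 × 20 = 80 of 5 × 20 = 100 planned minutes. This applies to the active arm only, because sham delivers just brief ramps at the start and end.

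**Step 3: who could have no reading after the start.** UH3: 0.20 × 100 = 20 lost over the sessions and first two scans. The share lost before session 5 is not given, so the range is 0 to 20. If allocation and attrition are equal by arm (an assumption), 20 / 2 = 10, so about 0 to 10 are in the active arm. The UG3 figure of 20% is described as data loss from poor performance or movement, so it is not used to count early stoppers.

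**Step 4: does week 2 follow the last session?** The documents do not say what week 2 is counted from.

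- Counted from session 1 as day 0: session 5 falls on day 4 (consecutive days) to day 9 (10-day course). Day 14 is then 14 − 4 = 10 to 14 − 9 = 5 days later.
- Counted from baseline, with session 1 on day s: session 5 falls on day s + 4 to s + 9. For it to precede day 14, s must be at most 9 (consecutive days) or at most 4 (10-day course).

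Week 2 could therefore fall before session 5 under the second reading, and the fix needs a timing rule.

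**Step 5: do the other measures fill the gap?** As described, none is a mania screen with a threshold after the last session. The side-effects form asks how bothersome each symptom is and is last given right after session 5. It is my inference that elevated mood may not be felt as bothersome and that later onset would be missed. SAFTEE is described only at sessions. The week 2 PANAS informs study-physician judgement but has no numeric cut-off.

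**Step 6: cost.** 60 + 100 = 160 forms at most. The documents give no false-positive rate. At an assumed 1% to 10%, 0.01 × 160 = 1.6 and 0.10 × 160 = 16, so about 2 to 16 evaluations.

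**The case against.** The strongest reply is that the schedule fits its purpose. The ASRM is meant to protect participants during the intervention, and a reading before session 5 can still stop a dose, while a reading after the course cannot. At-risk histories are excluded, mood is asked about after every session including the fifth, and the week 2 PANAS feeds a physician's decision. On this view the point is a wish for one more form, with no demonstrated benefit.

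Much of this stands. A reader might infer that the plan contradicts itself or leaves mood unmonitored after session 5. The documents do not support that, because the PANAS, the side-effects form and physician oversight form a real pathway, although one without a mania cut-off. A reader might also infer that the fix gives early stoppers an on-treatment reading. It does not: it gives a reading after treatment, and only in those who attend. They may be few, since this group is drawn from those expected to be lost.

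Nor can a case count be drawn from the cited depression trial, with 7 of 120 participants developing mania or hypomania. Five of the seven were in the group that also received sertraline, and the protocol says that the cause is unknown.

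The reply does not remove the point. Session 5 and early stoppers' exposure lie within the intervention period, yet no ASRM follows either. A positive result after the course can still be acted on, because the plan provides for additional mental health treatment as well as discontinuation.

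**Conclusion.** The point holds as a minor, inexpensive improvement, not as an error. As described, the ASRM is the only mania-specific measure with an action cut-off. It gives completers one reading after stimulation starts and none after the full course, and it gives early stoppers none after the start. In UH3, 0 to 20 participants could lack any reading after the start.

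Two assumptions matter. The active-arm range of about 0 to 10 needs equal allocation and attrition. The statement that no other mania screen exists rests on the instruments as described, since not every item of the side-effects form or SAFTEE is listed. The number of hypomania cases that would be found cannot be estimated, because the documents give no rate attributable to tDCS.

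**What to change.** Add the ASRM at the existing week 2 assessment in both phases, with the existing cut-off of 6 or more and the existing clinician evaluation. State that it is given after session 5, or after the last session received in those who stop early. If week 2 falls sooner, give it at the next scheduled contact, for example the post-course scan in UG3 or the week 4 assessment in UH3.

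The cost is at most one short self-report form per participant at a contact already planned, plus the false-positive evaluations estimated above. No new visit is needed, and no endpoint, analysis or stopping rule changes.
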